 18. DRUGS OR DEVICES
19. REFERENCES

1. OBJECTIVES/SPECIFIC AIMS

1.1 Introduction and Context

Opioid use disorder (OUD) has rapidly become a public health epidemic despite existing opioid substitution pharmacotherapies. In 2016, an estimated 11.5 million Americans misused prescription opioids and 948,000 people used heroin, representing a 500% increase since 1999 (Centers for Disease Control, 2018). This is highly concerning, as opioids are responsible for over 2/3 of all drug overdose deaths and in 2017, one person died approximately every 11 minutes of opioid overdose (Centers for Disease Control, 2018). The high incidence of heroin use (there were 170,000 new heroin users in 2016) is also problematic given the risk of blood-borne infections including HIV and HCV (Health and Human Services, 2018). The opioid epidemic is overall estimated to cost 504 billion dollars annually (Council of Economic Advisors, 2017).

1.2 Description of Current Standard of Care

All currently approved pharmacotherapies for OUD act as either agonists (i.e. methadone), antagonists (i.e. naltrexone), or partial agonists (i.e. buprenorphine) at the mu-opioid receptor. Successful induction rates onto extended release opioid antagonist therapies such as monthly extended release naltrexone injection are low (40-46%, Bisaga et. al., 2018). Furthermore, rates of relapse at 24 weeks (defined 7 days of self-reported opioid use or 4 consecutive weeks of positive urine toxicology screens) are high for both monthly injections of extended release naltrexone (65%) and self-administered daily oral buprenorphine-naltrexone (57%, Lee et al., 2018). Similarly, comparisons of daily methadone vs buprenorphine found mean opioid relapse rates after 13 weeks of treatment of approximately 40%, with no between-group differences (Mattick et al., 2003). These findings suggest room for improvement using novel treatment approaches (Connery et al., 2015).

1.3 Purpose and Objectives of the Study

The primary objective of the proposed study is to directly address this critical need by preliminarily testing the efficacy of ketamine in reducing opioid use and depression symptoms among individuals (N=30) with concurrent OUD and MDD who have failed to maintain abstinence despite treatment with a standard of care pharmacotherapy for OUD (i.e. buprenorphine, methadone or naltrexone). Effects on related symptoms and psychiatric conditions (e.g., cravings, motivation to quit, and anxiety symptoms) will also be explored. To accomplish this, we will use an intent-to-treat, double-blind, randomized clinical trial to compare the efficacy of ketamine to placebo control over a twice-weekly treatment schedule for four weeks. We will examine standardized, repeated dependent measures of clinical outcomes at baseline and multiple time points after the first treatment (48h to 8 weeks post initial treatment) with primary outcomes assessed at one month following the first treatment.

1.4 Specific Aims

To achieve these objectives, the following Specific Aims are proposed:

Specific Aim 1: To demonstrate the feasibility of study recruitment and completion of the treatment protocol.

Specific Aim 2: To preliminarily assess the efficacy of ketamine, as compared to placebo, in reducing OUD severity (i.e., percent days using opioids, abstinence rates) as measured by the Timeline Followback and urine drug screen tests.

Specific Aim 3: To preliminarily assess the efficacy of ketamine, as compared to placebo, in reducing symptoms of depression using the Montgomery–Asberg Depression Rating Scale.

2.0 BACKGROUND

Role of Depression in Maintaining Abstinence From Opioids

Negative affect has been found to be a key mediator in failure to achieve abstinence and depression is a frequent comorbidity in OUD. Nearly two out of three persons entering treatment for opioid detoxification screen positive for depression, however 48% of those meeting criteria for depression had not perceived a need for treatment (Brienza et al., 2000; Stein, 2017; Volkow, 2004). However, desire for improvement in mood is the most commonly cited reason for relapse in OUD following initial addictions treatment (Kadam et al., 2017; Huhn et al., 2018; Volkow et al., 2019). In addition to contributing to relapse and being a risk for unintentional overdose, OUD is an independent risk factor for completed suicide (Volkow et al., 2019). A national cohort study of veterans (n=4,863,086) found that after controlling for psychiatric and medical comorbidities, overall substance use was still associated with a 1.67 hazard ratio for suicide in men and 2.15 in women (Bohnert et al., 2017). Furthermore, in women, OUD was associated with the highest hazard ratio for suicide of any substance of abuse at 2.33 (Bohnert et al., 2017).

Glutamatergic Dysregulation Contributes to Both Depression and Addiction Pathology

Glutamatergic dysregulation in the prefrontal cortex and mesolimbic regions (including the amygdala and the nucleus accumbens) has been implicated in addiction pathology across multiple substances of abuse (Gass & Olive, 2008; Markou et al., 1998). Similarly, depression has been shown to have aberrant glutamate signaling (Abdallah et al., 2017; Murrough et al., 2017; Niciu et al., 2014). On a cellular level, astrocytes are responsible for maintaining glutamate homeostasis (Parpura and Verkhratsky, 2012) and both depression and addiction have been linked to impaired ability of astrocytes to upregulate glutamate (Rajkowska et al., 2013; Scofield et al., 2014). Ketamine is a noncompetitive antagonist of NMDA glutamatergic receptors which has been widely used for pain control in conjunction with general anesthesia since it was FDA approved in 1970.

Clinical Trials for Depression Treatment

Results from several meta-analyses indicate that ketamine can induce ultra-rapid improvements in depression and suicidality (Han et. al., 2016; Wilkinson et. al., 2017). This remission is most enduring in individuals with a family history of substance use disorders (Niciu et al., 2014). It is widely accepted that all currently approved pharmacotherapy classes for depression (serotonin reuptake inhibitors, monoamine oxidase inhibitors, and tricyclic antidepressants) are associated with a delayed onset of anti-depressant activity of 2-4 weeks. A meta-analysis of nine high-quality studies showed that ketamine was significantly more effective than placebo in reducing symptoms of major depressive disorder at 24 hours, 72 hours, and 7 days post-infusion (Han et. al., 2016). Additionally, results from a recent meta-analysis of ten clinical trials showed accumulating evidence that ketamine can significantly reduce suicidal ideation within 24 hours with moderate to large effect sizes (Wilkinson et. al., 2017). The overall duration of anti-depressant response was found to last between 3-12 days (Andrade, 2017). However, in a subgroup analysis, positive family history of alcoholism was found to be associated with a significantly longer duration of anti-depressant efficacy, averaging 17 days for the family history positive group and 3.6 days for the family history negative group (Niciu et. al., 2014). This suggests that the genetics underlying substance use confer a stronger response to the effects of ketamine.

Clinical Trials for Substance Use Disorder Treatment

Ketamine has shown early evidence of efficacy in the treatment of substance use disorders. One study evaluating the adjunctive use of ketamine in heroin use disorder showed that a single-session of highdose (2 mg/kg IM) ketamine demonstrated one-month abstinence rates of 85% compared to 55% abstinence in the low dose group (0.2 mg/kg IM), and one-year abstinence rates of 24% in the high dose group as compared to 6% in the low-dose control group (Krupitsky et al., 2002). In a follow-up study comparing three repeated sessions of ketamine infusions with concurrent psychotherapy to single-session treatment, abstinence rates were increased to 50% in the 3 session group as compared to the single session rate of 22% (Krupitsky et al., 2007). Related studies found that ketamine is useful as an adjunct to psychotherapy in the treatment of alcohol use disorder (Krupitsky and Grinenko, 1997) with one-year complete abstinence rates of 65.8% in the ketamine-assisted psychotherapy group compared to 24% in the control psychotherapy group. Intriguingly, the anti-depressant response to ketamine occurs primarily after the drug has been cleared from the body, suggesting that its primary effects are mediated through downstream processes. Ketamine has also been shown in a randomized controlled trial to facilitate rapid-opioid induction under general anesthesia, with significant improvements in clinical and subjective opioid withdrawal symptoms (Jovaisa et. al., 2006). More recently, ketamine has been studied in cocaine use disorder and found to improve levels of motivation to quit using and to reduce cocaine craving (Dakwar et al., 2014) and reduce rates of cocaine self-administration by 67% relative to baseline (Dakwar et al., 2017; Dakwar et al., 2018). Ketamine has been studied as an adjunct agent to benzodiazepines for acute alcohol withdrawal and has been found to reduce supplementary diazepam equivalent requirements by 40 mg at 12 hours post-ketamine initiation while maintaining equivalent levels of withdrawal symptoms between groups (Wong et al., 2015).

Novelty and Importance of the Current Study

While non-controlled trials for heroin and small pilot trials for other substance of abuse have shown evidence that ketamine improves abstinence rates and motivation to quit while reducing cravings, there are no completed randomized controlled trials evaluating the efficacy of ketamine in increasing abstinence in OUD.

3.0 INTERVENTION TO BE STUDIED

3.1 Overview of Study Medication

Ketamine was originally FDA approved in 1970 for pain control in conjunction with general anesthesia (Ketalar, 2018). The drug has since been evaluated in academic settings for the treatment of pain and a multitude of psychiatric indications. Ketamine has been increasingly studied in academic settings and used off-label in private practice settings over the past 10 years (Wilkinson et al., 2017). Ketamine undergoes extensive hepatic first pass metabolism, with an oral bioavailability of approximately 16% (Mathew et al., 2012). For induction of anesthesia, doses of 1 to 4.5 mg/kg IV or 6.5 to 13 mg/kg IM are recommended (Ketalar, 2018).

3.2 Safety and Toxicity

The acute toxicity of ketamine has been studied in multiple species. In mature mice and rats, the intraperitoneal LD50 values have been shown to be approximately 100 times the average human intravenous dose (Ketalar, 2018). Repeated, daily intravenous injections have been studied in rats, and dogs for as long as 6 weeks with excellent tolerability (Ketalar, 2018). Similarly, twice weekly treatments in monkeys over a four- to six-week period were well tolerated (Ketalar, 2018). At sub-anesthestic doses in human clinical trials for depression, the most clinically significant physical adverse event from ketamine is a transient increase in blood pressure, which was experienced by 29.8% of participants with a mean systolic blood pressure increase of 19.6 mmHg (p<0.001) and a mean diastolic blood pressure increase of 13.4 mmHg (p<0.001, Wan et al., 2015). Small, but statistically significant changes in perception (including derealization, depersonalization, distortion of time and space, and sense of illusion) were categorized as "feeling strange or unreal" and were experienced by 11.7% of participants (Wan et al., 2015). The average peak score of 4.5 on the Brief Psychotic Rating Scale is consistent with very mild symptom severity (Wan et al., 2015).

3.3 Study Drug, Dose, Mode of Administration and Justification

Ketamine is concentrated at a dose of 50mg/ml and will be administered by intramuscular administration in the amount of 60 mg (1.2 ml). This dose follows the FDA-dosing guidelines of a maximum dose of 60 mg per treatment day, with a lifetime maximum of 8 treatments for psychiatric indications. Each study drug administration will be directly observed by the PI. For a 75 kg person, this dose will translate into an effective dose of 0.74 mg/kg based on an intramuscular bioavailability of 93%. While formal dose response studies for depression are lacking, ketamine has been most widely studied for psychiatric indications at 0.5 to 1.0 mg/kg given intravenously. Although there are only a few studies evaluating the use of ketamine in the treatment of substance use disorders, doses in these trials have ranged from 0.5 to 0.8 mg/kg given intravenously or 2 mg/kg given intramuscularly (Jones et al., 2018).

3.4 Placebo Drug, Dose and Mode of Administration

A visually identical sterile saline control injection of equal volume will be also administered intramuscularly.

4.0 STUDY ENDPOINTS

4.1 Primary Outcomes

Primary outcomes will be 1) the percentage of individuals completing informed consent out of the number of individuals eligible on the initial screening and 2) the percentage of individuals that complete informed consent which complete the full protocol.

4.2 Secondary Outcomes

Secondary outcomes will include changes in depression severity (as measured on the Montgomery– Asberg Depression Rating Scale), which will be calculated as a change from baseline to 4-week followup.

Montgomery Asberg Depression Rating Scale (MADRS; Montgomery, 1979). The MADRS is a clinician administered, 10-item questionnaire of depression severity. The total score ranges from 0-60, with scores of 0-6 considered normal (non-depressed), 7-19 indicative of mild depression, 20-34 indicative of moderate depression, and 35-60 indicative of severe depression. Individuals scoring 20 or higher on the MADRS will be included in the study. The MADRS evaluates the following symptoms of depression: 1) clinical appearance of sadness, 2) self-reported sadness, 3) inner tension, 4) reduced sleep, 5) reduced appetite, 6) concentration difficulties, 7) lassitude, 8) inability to feel, 9) pessimistic thought process, and 10) thoughts of suicide. The MADRS has a sensitivity of 94% and a specificity of 83%, has been shown to have high internal consistency, and correlates well with other measures of depression such as the Hamilton Depression Scale.

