10. STUDY DESIGN/METHODS

10.1 Study Overview

This is a double blind, placebo-controlled trial to assess the efficacy and safety of twice weekly intramuscular injections of ketamine in decreasing symptoms of OUD and MDD. Subjects will participate in a baseline visit to complete informed consent as well as complete assessments to evaluate study

eligibility and collect baseline data. Eligible participants will return within one week for the initial ketamine intervention procedure. Immediately prior to the interventional procedure, participants will be guided through a mindfulness-based exercise to facilitate relaxation and reduce anxiety during the intervention. Participants will be subsequently monitored for 120 minutes, during which time they will complete measures assessing their perception of the interventional experience. Participants initially assigned to the placebo group may choose to optionally complete 8 ketamine medication sessions beginning in Study WK #5.

	Groups A & B							
Visit #1: Baselir	ne Assessments		Study WK #0					
Visit #2: 1st Tx	Visit #3: 2nd Tx		Study WK #1					
Visit #4: 1st Tx	Visit #5: 2nd Tx		Study WK #2					
Visit #6: 1st Tx	Visit #7: 2nd Tx		Study WK #3					
Visit #8: 1st Tx	Visit #9: 2nd Tx		Study WK #4					
Visit #10: 1 WK follow-up	Visit #10: 1st KET Tx	Visit #11: 2nd KET Tx	Study WK #5					
Group A (Ketamine)		Placebo): Optional Visits						
Visit #11: 2 WK follow-up	Visit #12: 3rd KET Tx	Visit #13: 4th KET Tx	Study WK #6					
	Visit #14: 5th KET Tx	Visit #15: 6th KET Tx	Study WK #7					
Visit #12: 4 WK follow-up	Visit #16: 7th KET Tx	Visit #17: 8th KET Tx	Study WK #8					
	Visit #18: 1 WK follow-up		Study WK #9					
	Visit #19: 2 WK follow-up	2	Study WK #10					
		2 2	8					
			l					

Visit #20: 4 WK follow-up

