10.3 Schedule of Assessments

The instruments to be used are standardized, have good psychometric properties, and are widely used. The schedule of study assessments is provided in **Table 2**.

Table 2: Schedule of Assessments

Table 2. Schedule of Assessments			TIME POINT										
Instrument Name	Purpose	Wk 0			(Wk6)					Wk 5 (9)	Wk 6 (10)	Wk 8 (12)	
		BL	Tx1	Tx2	Tx3	Tx4	Tx5	Tx6	Tx7	Tx8	1W F/U	2W	4W
Self-Reports and Consent											170		
Informed Consent X													
Demographics Form	Sample characterization	Х											
Concurrent Medications Form	Monitor medications	Х	Х	Х	Х	Х	Х	Х	Х	Х	Х	Х	Х
Treatment Services Tracking Form	Assess treatment engagement	х	Х	Х	Х	Х	Х	х	х	Х	Х	х	х
*Time Line Follow-Back (TLFB)	Primary Outcome: opioid use (amt. and frequency)	х	х	х	х	Х	Х	х	х	х	х	х	х
Beck Depression Inventory-II	Self-reported assessment of depression symptom severity	х	х	х	Х	Х	Х	х	х	х	х	х	х
Visual Analog Scale (VAS)	Measure subjective levels of opioid craving	х	Х	х	х	Х	Х	х	х	х	Х	Х	Х
General Anxiety Disorder (GAD-7)	Self report of anxiety symptom severity	х	Х	х	х	Х	Х	х	х	х	Х	Х	Х
Mystical Experiences Questionnaire	Measure of perceptual experiences		Х	Х	Х	Х	Х	х	х	Х			
Brief Pain Inventory	Measure of pain and quality of life	х		х		Х		х		х			х
University of Rhode Island Change Assessment (URICA)	Measure of motivation for change	х		х		х		х		х			х
Insomnia Severity Index (ISI)	Assess insomnia and sleep quality	х		х		Х		х		х			х
Five Facets of Mindfulness (FFMQ)	Assess aspects of mindfulness related	х		х		Х		х		х			х
PTSD Checklist (PCL-5)	Measure of PTSD symptoms	х		х		Х		х		х			х
Fagerstrom Test of Nicotine Dependence (FTND)	Measure of nicotine dependence	Х		х		Х		Х		х			х
Assessment of the Blind	Participant Perception of Randomization									Х			
Study goals	To characterize goals for treatment	х	х	х	х	Х	х	х	х	х			
	CI	inician	Assess	ments	n	1	1	1		1	n	n	
History and Physical Exam	Eligibility assessment	Х											
Vital Signs Measurement	Obtain readings of blood pressure, pulse, temperature, respirations and pulse oximetry	х	X*	X*	X*	X*	X*	X*	Х*	X*	х	х	х
Modified Observer Alertness/Sedation Scale (MOASS)	Measure of sedation		х	х	х	х	х	х	x	х	х		
Clinical Opioid Withdrawal Scale (COWS)	Clinician assessment of opioid withdrawal symptoms	Х											
*Montgomery-Asberg Depression Rating Scale (MADRS)	Primary Outcome: Clinician assessed measure of depression symptom severity	х		х		х		х		х	х	х	х

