12.0 DATA MANAGEMENT

12.1 Data Analysis Plan

Baseline demographic characteristics will be collected and descriptive statistics will be used to characterize participants. Data will be collected and managed using the secure REDCap (Research Electronic Data Capture) database. Descriptive statistics for primary outcomes will include 1) the percentage of individuals completing informed consent out of the number of individuals eligible on the

initial screening and 2) the percentage of individuals that complete informed consent which complete the full protocol. Other descriptive statistics for the sample population will be analyzed, and baseline characteristics that are found to be significantly associated with other outcome measures will be included as covariates. Spaghetti plots will be produced to guide modeling outcomes as a function of time. All analyses will be conducted based on intention to treat. Subjects assigned to Group B (placebo) who complete Study Wk4 (at which time main outcomes are assessed), may choose to receive 8 ketamine treatments before completing follow-up visits. To preserve study blinding, subjects who are among the final 6 subjects being enrolled will not be unblinded until primary outcomes are assessed for all 30 subjects.

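### The MADRS time point is labelled inconsistently (Wk 4 or Wk 8/12), no rule keeps placebo subjects' ketamine data after Wk 4 out of the interaction and plateau analyses, and the detectable difference given for one month is really a seven-measurement average

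*Combined protocol and SAP*

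**What the plan says.** **Time point.**
- Section 4.2 takes the MADRS change "which will be calculated as a change from baseline to 4-week followup".
- The visit figure in section 10.1 uses that label twice: "Visit #12: 4 WK follow-up" for Group A, on the Study Wk 8 row, and "Visit #20: 4 WK follow-up" for placebo subjects after the optional course, at Wk 12. The last column of Table 2 is headed Wk 8, with 12 in brackets.
- Section 1.3 has "primary outcomes assessed at one month following the first treatment". Sections 12.2 and 12.3 also say one month.
- Section 12.1 places the main outcomes at Study Wk 4, in the sentence that offers crossover: Group B subjects who "complete Study Wk4 (at which time main outcomes are assessed), may choose to receive 8 ketamine treatments before completing follow-up visits".

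**Crossover.** Section 10.1: "Participants initially assigned to the placebo group may choose to optionally complete 8 ketamine medication sessions beginning in Study WK #5".

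**Analysis.** The general rule in section 12.1 is "All analyses will be conducted based on intention to treat". Section 12.2 makes the group-by-time interaction and a post-hoc comparison at one month the main hypothesis, with time in days and no stated window. A secondary analysis looks for a plateau in ketamine's effect over 8 weeks.

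**Sample size.** Section 12.3 gives a detectable MADRS difference of 14.4 at one month with 15 per arm, and 16.1 with 12 per arm. It assumes seven repeated measurements, AR(1) correlation 0.9, SD 15.8, 80% power and a 0.05 level. It does not list the seven.

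**The concern.** Read literally, section 4.2 puts the outcome at a visit that placebo subjects who switch reach only after eight ketamine sessions, and at different calendar weeks for different subjects (Wk 8 or Wk 12).

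Fixing the endpoint at Wk 4 does not remove the second difficulty. Intention to treat keeps each subject in the assigned arm. It does not say whether ratings after crossover are included, censored or realigned to the second course. If they enter the interaction or plateau model by assigned arm, ketamine exposure is counted as placebo. A narrowing difference, or an apparent plateau, could then not be told apart from placebo subjects starting ketamine.

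Third, the stated detectable difference does not belong to the comparison it is attached to. MADRS is a secondary outcome in a feasibility pilot, but section 12.3 says the study is powered on it.

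**Working it through.** **1. MADRS ratings by Wk 4.** Table 2 marks MADRS at baseline, Tx2, Tx4, Tx6, Tx8 and the 1-, 2- and 4-week follow-ups: 8 ratings, 7 of them after baseline. By Wk 4 there are 5 including baseline, 4 without it. Seven MADRS ratings therefore cannot be reached before crossover opens.

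**2. Reproducing section 12.3.** Two-sided 0.05 and 80% power give the multiplier 1.960 + 0.842 = 2.8016. For the mean of m AR(1) measurements:

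- V = Σ 0.9^|i−j| / m². For m = 7, V = 39.093/49 = 0.7978.
- SE = 15.8 × √(V × 2/n) = 5.153 (n = 15) or 5.761 (n = 12).
- Detectable difference = 2.8016 × SE = **14.44** or **16.14**.

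These match the plan's 14.4 and 16.1. Variants that do not match both:

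| Variant | 15 per arm | 12 per arm |
|---|---|---|
| Single time point, two-sided | 16.16 | 18.07 |
| Single time point, one-sided | 14.35 | 16.04 |
| Average of 4 measurements | 15.17 | 16.96 |
| Average of 5 measurements | 14.92 | 16.68 |
| Average of 7, t distribution | 14.96 | 16.89 |

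The one-sided single-visit version comes close but misses both figures.

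**3. Detectable difference at Wk 4** (SD 15.8, two-sided, 80% power).

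*Unadjusted contrast:* 2.8016 × 15.8 × √(2/n) = 16.16 or 18.07. Power for 14.4 is Φ(14.4/5.769 − 1.96) = 70% with 15 per arm and Φ(14.4/6.450 − 1.96) = 61% with 12.

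*Using baseline.* This assumes that the per-rating correlation extends back to baseline, four ratings before Tx8. Multiply the unadjusted value by √(2(1−r)) for the change score, or by √(1−r²) with baseline adjustment.

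| Correlation per rating | r, baseline to Wk 4 | Change score: 15 (12) per arm | Baseline-adjusted: 15 (12) per arm |
|---|---|---|---|
| 0.9 | 0.9⁴ = 0.656 | 13.4 (15.0) | 12.2 (13.6) |
| 0.8 | 0.8⁴ = 0.410 | 17.6 (19.6) | 14.7 (16.5) |

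For example, at 0.9 the change score gives 16.163 × 0.8293 = 13.40. At 0.8 the adjusted analysis gives 16.163 × 0.9123 = 14.745.

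**4. Illustration of crossover.** The documents give no uptake, so c (the share of Group B that switches) is assumed, and switchers are assumed to gain the full effect.

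- *Difference by assigned arm at Wk 8*, if the effect stays at 14.4: 14.4 × (1 − c) = 10.8, 7.2 or 0 at c = 25%, 50% or 100%. The curves converge although ketamine's effect has not changed.
- *Seven-visit average*, if the seven are all the post-baseline ratings (3 of 7 after crossover opens) and the effect is constant: 14.44 × (7 − 3c)/7 = 12.9, 11.3 or 8.25. Power, Φ(difference/5.153 − 1.96), falls from 80% to 71%, 60% or 36%.

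**The case against.** **The label is a slip.** This is probably right. Section 12.1 fixes Study Wk 4 in the same sentence that offers crossover. Section 1.3 counts time from the first treatment, and sections 12.2 and 12.3 speak of an 8-week follow-up period that appears to do so too. On that usage, section 4.2 means four weeks from first treatment. A reader might infer that the sponsor deliberately set a contaminated Wk 8 endpoint; the documents do not support that. But sections 10.2 and 10.6 use follow-up for the weeks after treatment, and the visit tables attach this exact label to Wk 8 or 12, so the text still needs reconciling.

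**Intention to treat already governs, and the planned contrast is at one month.** The one-month comparison is indeed largely protected, and fully so if it is a Wk 4 contrast with time as categories. The interaction is also part of the main hypothesis, however, and has no window. Assigned-arm analysis is what produces the misattribution, so the rule does not cure it. The contents page lists a section on handling missing data that is not in the body supplied. Such a section would not necessarily cover ratings that are observed after crossover.

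**The plateau model is secondary and only to be considered.** True, and it concerns ketamine's effect rather than explicitly a difference between arms. The plan still does not say whose data enter it.

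**Seven may be a generic design parameter.** This stands. Section 12.3 uses the same seven time points for opioid use, which Table 2 marks at every visit. A reader might infer that the power calculation relies on ratings after crossover; the plan does not state that.

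**The loss of power is assumed.** This also stands. Uptake, the gain in switchers and the visit list are all assumptions, and section 2.0 cites an antidepressant response lasting 3–12 days, so a held effect cannot be taken for granted.

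**Conclusion.** The point holds in three parts.

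1. Section 4.2 conflicts with sections 1.3, 12.1, 12.2 and 12.3 on when MADRS is assessed. Wk 4 is the likely intention.
2. With the endpoint at Wk 4, the interaction and the 8-week plateau analysis still lack a rule for Group B data after crossover. Run by assigned arm on all data, they mix a placebo-controlled comparison with ketamine in both arms. A categorical-time Wk 4 contrast is not affected.
3. The figures 14.4 and 16.1 are not detectable differences at one month. Among the versions tried, they match only a seven-measurement average.

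The size that can be stated firmly is for an unadjusted Wk 4 contrast at the plan's SD: 16.2 with 15 per arm or 18.1 with 12. Whether using baseline brings this below 14.4 depends on a correlation the plan does not justify: 13.4 or 12.2 with 15 per arm at 0.9 per rating, but 17.6 or 14.7 at 0.8. It would therefore be wrong to conclude either that a Wk 4 analysis is necessarily weaker than stated or that it is at least as good. The crossover figures are illustrations and do not predict the trial's power.

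This should be fixed. It does not touch the feasibility outcomes that section 4.1 names as primary.

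**What to change.** 1. In section 4.2 and Hypothesis 1, name one pre-crossover MADRS visit as the endpoint and align the one-month wording with it. The last scheduled candidate is Visit 9 (Tx8). Two features should be stated. Section 10.6 places assessments before dosing, so this rating precedes that session's injection. With Tx1 in Study Wk 1 and Tx8 in Study Wk 4, it also falls slightly short of one month after first treatment.
2. Use the same cut-off for Hypothesis 2.
3. Fit the randomized comparison to baseline and pre-crossover visits only, preferably with time as categories.
4. Report later data descriptively by arm. Run the plateau model in Group A only, or with Group B censored at crossover.
5. Restate section 12.3 for the chosen analysis. List the visits, and state the correlation, sidedness and whether baseline is adjusted for.

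**Cost.** Changes to wording and a revised sample-size paragraph; no new visits. The randomized MADRS model has fewer time points (5 including baseline), and the stated detectable difference may become less favourable. Opioid use loses little: Table 2 marks the Timeline Followback at baseline and at all eight treatment visits, so 9 time points remain before crossover.
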